5.5 Derived Variables

All questionnaire scores will be derived by Biostatistics in the ADaM datasets using the formulas defined below, even if calculated scores are present in the EDC database. All pre-calculated scores will be ignored for analysis.

- With the following exception, vIGA-AD Success = vIGA-AD of ‘Clear’ (0) or ‘Almost Clear’ (1) plus at least a 2-grade improvement from Baseline. The exception is that for subjects who discontinued early from study due to an AE or lack of efficacy, the subject will be considered as not having a vIGA-AD success (for MI and non-responder imputation analyses) or missing (for observed case analyses) for all pre-specified analysis visits (refer to Section 5.4) for which the subject’s last dose day falls within analysis visit window or is prior to the start of the analysis visit window.
- Average weekly WI-NRS = Average weekly WI-NRS pruritus score will be calculated as the sum of the daily WI-NRS scores reported during a specific week (in a 7-day period; refer to Section 5.4) of the study divided by the number of days with non-missing scores for that week. A minimum of 4 days of observations are needed to calculate an average weekly WI-NRS pruritus score. Otherwise, the corresponding average weekly WI-NRS pruritus score will be considered missing.
- With the following exception, a WI-NRS success = achievement of a 4- point reduction in average weekly WI-NRS pruritus score compared to average weekly WI-NRS baseline, calculated only for the subjects with average weekly WI-NRS score of ≥ 4 at baseline. The exception is that for subjects who discontinued early from study due to an AE or lack of efficacy, the subject will be considered as not having a WI-NRS success (for MI and non-responder imputation analyses) or missing (for observed case analyses) for all pre-specified analysis visits (refer to Section 5.4) for which the subject’s last dose day falls within the analysis visit window or is prior to the start of the analysis visit window.
- EASI total score = $0.2 (E_h + I_h + Ex_h + L_h) A_h + 0.2 (E_u + I_u + Ex_u + L_u) A_u + 0.3 (E_t + I_t + Ex_t + L_t) A_t + 0.3 (E_l + I_l + Ex_l + L_l) A_l$

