6.2.1 Multiple Imputation

All subjects, regardless of completion status, will have available data assigned to the pre-specified analysis visit using the analysis windows defined in Section 5.4, including the last available data of subjects who prematurely withdraws from the study. To comply with the definition of the primary estimand (Section 12.1.1), for subjects who discontinue due to lack of efficacy or adverse event, efficacy data assigned to a pre-specified analysis visit will be removed from the source data used for the multiple imputation process if subject's last dose day falls within the analysis visit window or is prior to the start of the analysis visit window used to assign data to a pre-specified analysis visit. This procedure will ensure that the data collected on or after these specific intercurrent events are not used in the imputation process.

For the primary efficacy endpoint of vIGA-AD success at Week 4 and the secondary endpoint of vIGA-AD success at Week 4 among subjects with a 'Moderate' randomized vIGA-AD score, the primary analysis will impute missing values using a Predictive Mean Matching (PMM) sequential-regression multiple imputation model for the ITT population. This is a three-step process.

1. The first step is to understand the pattern of missingness. In order to perform the multiple imputation, a monotone missing pattern has to be achieved. For example, if there exist values for baseline and Week 4 visits, but missing values for the Week 1 or 2 visits, the Markov-Chain Monte-Carlo (MCMC) method will be used to impute the small amount of missing data that may be missing at the intermediate visits that is required to make the missing data pattern monotone before applying the multiple imputation algorithm. This method uses a non-informative Jeffreys prior to derive the posterior mode from the expectation-maximization (EM) algorithm as the starting values for the MCMC method. The MCMC method will use the seed 6457149. The vIGA-AD score will be treated as a continuous variable for this step and the model will include the vIGA-AD scores at baseline, Week 1, Week 2, and Week 4. To avoid values that could not be observed in practice, imputed values will be rounded to the nearest integer (Round=1 option in PROC MI) in the range of 0 to 4.

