To determine the number of multiply-imputed datasets to be created at this step, the proportion of datapoints with non-monotone pattern across all visits and subjects will first be derived as follows:

$$\frac{\text{number of non monotone visits accross all visits and subjects}}{\text{total number of expected visits accross all subjects}} * 100$$

 Innovaderm Research ■■■	STATISTICAL ANALYSIS PLAN, Version 1.0
Protocol Number: ARQ-151-315	Sponsor: Arcutis Biotherapeutics, Inc.

Then, the following table will be used:

Non-monotone Missing Data	Number of Imputed Datasets
$\leq 2\%$	1
$> 2\% \text{ to } \leq 5\%$	3
$> 5\%$	10

2. Once the monotone pattern is achieved, the next step is to implement the imputation algorithm. For this, the PMM regression method will be used. This method is particularly helpful if the normality assumption is violated. For subjects with complete data up to a particular visit, a PMM regression model will be fit that includes the outcome at that visit as the dependent variable and as independent variables, the treatment group, and vIGA-AD score outcomes at previous visits, using a seed of 482371. For other scales/questionnaires, the actual baseline vIGA score will also be included as an independent variable. This process will be repeated 25 times, resulting in a total of 25 to 250 complete analysis datasets, depending on the number of imputed monotone datasets that are required. The seed may be changed after unblinding in case of any issues with the imputation process, and it will be documented in the CSR if any change is required.
3. For each of the 25 to 250 completed datasets, the necessary derived variable will be computed as defined in Section 5.5 and analyzed using a CMH analysis, adjusted for the randomized vIGA-AD score for the primary efficacy endpoint. The treatment effect on the secondary efficacy endpoint dealing with vIGA-AD success in the vIGA-AD moderate ITT population will be assessed with an unstratified chi-square test. Results will be combined into one multiple imputation inference as follows:

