 - a. Common proportion of success, common Mantel-Haenszel (MH) proportion difference (and associated 97.5% and 95% CIs), and common MH odds ratio (and associated common 97.5% and 95% CIs) will be combined using PROC MIANALYZE based on Rubin's rule. Common MH odds ratios and associated common 95% CI will first be normalized using a log-transformation before being combined using PROC MIANALYZE. The resulting combined common MH odds ratio and associated combined common 97.5% and 95% CIs will be back-transformed to the arithmetic scale before being presented in a table.
 - b. For the combined common proportion of success, the associated combined common 95% CI will be calculated as per Lott and Reiter multiple imputation

 Innovaderm Research ■■■	STATISTICAL ANALYSIS PLAN, Version 1.0
Protocol Number: ARQ-151-315	Sponsor: Arcutis Biotherapeutics, Inc.

Wilson interval method¹.

c. Two p-values will be produced for each analysis:

- i. The primary p-value will be obtained from a multiple imputation CMH test, where CMH general association statistics and their standard errors obtained from the analysis of each multiply-imputed dataset will be transformed as per Wilson-Hilferty² before being combined using PROC MIANALYZE based on Rubin's rule. Because the Wilson-Hilferty transformation is a monotone transformation, the p-value for the CMH test is the one-sided p-value from the t distribution. This p-value will be the primary p-value used to evaluate the result according to the multiple testing strategy described in Section 6.5.
- ii. Should the common MH odds ratio from the analysis of at least one of the multiply-imputed datasets be not estimable, combined common MH odds ratio and associated combined common CIs and p-value will not be presented. Under such circumstance, conclusions will be based on the p-value obtained from a multiple imputation test of the proportion difference, where the common proportion difference using MH weights and associated common standard errors based on the Sato variance estimator obtained from the analysis of each multiply-imputed dataset will be combined using PROC MIANALYZE based on Rubin's rule.

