6.5 Multiple Comparisons/Multiplicity

To control for familywise type I error at level of 0.025, the secondary efficacy endpoints will be tested sequentially at an alpha level of 0.025 upon successful demonstration of statistical significance for the primary endpoint. The order of the secondary efficacy endpoints is important. Should, anywhere during the sequential testing of secondary efficacy endpoints, there is a p-value >0.025 , further testing results are considered “not statistically significant” regardless of the p-value computed.

Figure 2 Multiple Testing Scheme

Achievement of vIGA-AD success is a score of “clear” or “almost clear” plus a 2-grade improvement from baseline.

EASI-75: achievement of at least a 75% reduction in the Eczema Area and Severity Index

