12.1.3 Primary Endpoint Analysis

For the primary analysis, missing vIGA-AD scores will be imputed using multiple imputation as described in Section 6.2.1. These imputations will result in a minimum of 25 to a maximum of 250 complete analysis datasets, depending on the number of imputed monotone datasets that are required.

Percentages of subjects having a vIGA-AD Success (refer to Section 12.1.1) will be presented by visit and treatment group based on multiply imputed data in the ITT population along with both 97.5% and 95% Wilson CIs. The common MH odds ratio and common MH proportion difference, adjusted for the randomization factor (i.e., randomized vIGA-AD score) will also be provided along with their common associated 97.5% and 95% CIs. Additionally, count and percentage of subjects having a vIGA-AD success, count and percentage of subjects in each category of the vIGA-AD scale, and descriptive statistics for the vIGA-AD scores, change in vIGA-AD score from baseline and percent change in vIGA-AD score from baseline will be presented by visit and treatment group based on observed data in the ITT population.

The primary endpoint (vIGA-AD Success at Week 4) will then be analyzed using multiple imputation CMH test stratified by randomized baseline vIGA-AD. To do so, a CMH analysis will be performed separately for each of the complete multiply imputed analysis data sets, and results will be combined into one multiple imputation inference using the methodology described in Section 6.2.1. Statistical significance will be concluded at the 2.5% significance level (2-sided). Should the odds ratio be not estimable for at least one multiply imputed dataset, the conclusion of

 Innovaderm Research ■■■	STATISTICAL ANALYSIS PLAN, Version 1.0
Protocol Number: ARQ-151-315	Sponsor: Arcutis Biotherapeutics, Inc.

the study will be based on the p-value obtained from a MH test, stratified by randomized baseline vIGA-AD, for the common MH proportion difference at Week 4.

The following sensitivity and supplemental analyses to the primary analysis of the primary endpoint will be performed:

- Tipping Point analysis (refer to Section [6.2.3](#)) on ITT population.
- Non-responder imputation (refer to Section [6.2.2](#)) on ITT population.
- Observed data on ITT population (refer to Section [4.1](#)).
- Observed data on PP population (refer to Section [4.2](#)).

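### The SAP lets the seed of the primary multiple imputation be changed after unblinding for undefined issues: a small but avoidable choice in the test that gates all secondary endpoints

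*SAP*

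**What the plan says.** SAP 6.2.1 describes a three-step imputation.

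- **Step 1** uses MCMC to make the missing pattern monotone: "The MCMC method will use the seed 6457149". The number of data sets made here depends on skipped visits only: "the proportion of datapoints with non-monotone pattern across all visits and subjects will first be derived". The table then gives 1, 3 or 10 data sets for rates up to 2%, above 2% to 5%, and above 5%.
- **Step 2** runs predictive mean matching (PMM) 25 times per monotone data set with seed 482371, "resulting in a total of 25 to 250 complete analysis datasets, depending on the number of imputed monotone datasets that are required". It then adds: "The seed may be changed after unblinding in case of any issues with the imputation process". A change is to be documented in the CSR.
- **Step 3** pools the CMH statistics. Of the pooled CMH p-value it says: "This p-value will be the primary p-value used to evaluate the result according to the multiple testing strategy".

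SAP 6.5 makes that p-value the gate: "the secondary efficacy endpoints will be tested sequentially at an alpha level of 0.025 upon successful demonstration of statistical significance for the primary endpoint". SAP section 2 lists seven secondary endpoints, and SAP 12.2 imputes them in the same way as the primary.

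Two provisions limit the exposure. Under SAP 5.5, subjects who discontinue for an adverse event or lack of efficacy are fixed as non-responders from the affected visit on. SAP 12.1.3 adds non-responder and observed-data analyses, which use no random draws.

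**The concern.** A pre-specified seed ensures that nobody can pick among imputation results once treatment codes are known. The Step 2 sentence withdraws that assurance. It points to problems with the process, but no problem is defined, no replacement seed is named, nobody is named to decide, and a result already obtained under seed 482371 need not be shown. A CSR note saying the seed was changed would not tell a reader whether the verdict changed with it.

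Elsewhere the SAP does pre-specify a contingency properly. If the odds ratio cannot be estimated, 6.2.1 and 12.1.3 state the trigger and the fallback test. The seed has neither.

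The number of imputations bears on this. Monotone dropout, which Step 2 exists to impute, adds no draws. A trial with much dropout but few skipped visits stays at the minimum of 25 data sets, where dependence on the seed is greatest.

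At stake is a borderline primary result: a new seed could carry it across 0.025 and open or close the whole secondary sequence.

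**Working it through.** **Inputs.** From the documents: 433 active and 217 vehicle subjects (protocol synopsis); success 37% vs 22% (SAP 5.1); two-sided alpha 0.025, so critical z = 2.2414; M = 25×1 = 25, 25×3 = 75 or 25×10 = 250 data sets (SAP 6.2.1). Assumed: fraction of missing information (FMI) of 5%, 10% and 15%, because the documents give no missing rate.

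**1. The plan's power statement.** Pooled rate = (433×0.37 + 217×0.22)/650 = 0.3199. Standard error under the null = √[0.3199×0.6801×(1/433 + 1/217)] = 0.03880; under the alternative = √[0.37×0.63/433 + 0.22×0.78/217] = 0.03646. Power = Φ[(0.15 − 2.2414×0.03880)/0.03646] = Φ(1.729) = 95.8%. The SAP's claim of more than 90% holds.

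**2. Spread of p across seeds.** The between-seed SD of pooled z is √(FMI/M). For a seed-free p of 0.025, the 95% range is 2×[1 − Φ(2.2414 ± 1.96×SD)]. Example with FMI 10% and M = 25: SD = √(0.10/25) = 0.0632, z runs from 2.117 to 2.365, and p from 0.034 to 0.018.

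| M | FMI 5% | FMI 10% | FMI 15% |
|---|---|---|---|
| 25 | 0.020-0.031 | 0.018-0.034 | 0.017-0.037 |
| 75 | 0.022-0.029 | 0.021-0.030 | 0.020-0.031 |
| 250 | 0.023-0.027 | 0.023-0.028 | 0.022-0.028 |
| 500 (not in the plan) | 0.024-0.026 | 0.023-0.027 | 0.023-0.027 |

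**3. Type I error if the seed is changed once and the better result kept.** Integrate 1 − P(not significant | z)² over the null distribution of the seed-free z. Its variance is taken as 1 − FMI/M, so that a single seed has error of exactly 0.025.

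| M | FMI 5% | FMI 10% | FMI 15% |
|---|---|---|---|
| 25 | 0.0266 | 0.0273 | 0.0278 |
| 250 | 0.0255 | 0.0257 | 0.0259 |
| 500 | 0.0254 | 0.0255 | 0.0256 |

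**4. How often it could matter at the design effect (M = 25).** Expected z = (0.15/0.03646)×√(1 − FMI) = 4.11×√(1 − FMI).

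- The chance of landing in the seed range of step 2 is 1.5%, 2.5% and 3.7%. For FMI 10%: Φ(2.365 − 3.90) − Φ(2.117 − 3.90) = 2.5%.
- The chance that one re-seed turns failure into success is smaller: 0.21%, 0.36% and 0.53%.
- With the null standard error instead, z = 0.15/0.03880 = 3.87 before the same √(1 − FMI) factor, with SD 0.03646/0.03880 = 0.94. These become 2.0%, 3.3% and 4.8%, and 0.3%, 0.5% and 0.7%. The order of magnitude is unchanged.

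**5. Simulation checks.** Two separate simulations followed the SAP scheme (PMM with 5 donors, CMH stratified by Mild/Moderate, Wilson-Hilferty transformation, Rubin pooling, n = 650, monotone dropout only) with 5%, 10% and 15% assumed missing at Week 4.

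- *Near-threshold data sets, 6,000 draws each (4 per rate).* SD of p across seeds with M = 25: 0.002-0.003, 0.004-0.005 and 0.005-0.006. With M = 250: 0.0007-0.0011, 0.0012-0.0016 and 0.0013-0.0026.
- *Near-threshold data sets, 30 seeds each (4 per rate, M = 25).* SD of about 0.002, 0.003-0.006 and 0.004-0.007. One data set at 10% missing ran from p = 0.0205 to 0.0405, with a third of seeds at or below 0.025.
- *Null trials, 5,000 each at 5% and 10% missing.* Error was 2.2% and 2.3% with one seed, 2.5% and 2.7% with the best of 5, and 2.7% and 3.0% with the best of 10. The verdict differed among 10 seeds in 0.9% and 1.1% of trials.

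**The case against.** The strongest reply is that the clause means technical failure. If seed 482371 gives no valid output, there is no earlier p-value to choose from, and the first valid run keeps its nominal error. The inflated figures require a valid first result, a re-seed anyway and selection of the better one, which is not the stated purpose. That is probably the intent, but the text says any issues and does not require a failed run. Writing the intent down is what is asked.

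The size is also open to challenge, and much of that stands. FMI may be well below 5%: the trial lasts four weeks, the Week 4 window runs from day 23 to day 43 and admits early-termination data, the extension study requires the Week 4 visit, and discontinuations for adverse events or lack of efficacy are not left to the draws. At FMI 1-2% with 25 data sets, the step 3 formula gives about 0.0257-0.0260, and one re-seed rescues a failed trial about 0.1% of the time at the design effect. The simulated fixed-seed error was 2.2-2.3%, so a single re-seed may not take it above 0.025 at all.

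Finally, any change must be documented, and the analyses without draws would expose a result that depends on the seed. They would not replace the primary p-value. Deleting the clause would leave a true failure to be handled under SAP section 1, which requires deviations to be described and justified in the CSR. That is a stronger duty than documentation, and nothing is lost.

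**Conclusion.** The concern holds. The SAP expressly permits a choice after unblinding in the analysis that yields the confirmatory p-value, and nothing elsewhere in it narrows the trigger, names a replacement seed or requires the first result to be shown.

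The consequence is modest. Only a borderline result could change. One re-seed with selection adds about 0.002 to 0.003 to a 0.025 error rate at 25 data sets and less than 0.001 at 250; even the best of 10 seeds added only about 0.5 to 0.7 percentage points in simulation. If the design effect is true, the seed will rarely matter. These sizes rest on assumed FMI or missing rates and, for the simulations, on assumed outcome models and monotone dropout. The finding that the permission is open-ended does not depend on them.

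The change should be made because it is nearly free and protects the primary result in the one situation where it would be challenged.

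**What to change.** Delete the sentence in SAP 6.2.1 Step 2. Alternatively, replace it with a rule that:

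- limits a change to a stated technical failure, such as a program error or non-convergence;
- lists back-up seeds, in order, before unblinding;
- requires the result under seed 482371 to be reported if that run completed.

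State whether the same rule covers the Step 1 MCMC seed, since the present sentence stands in Step 2 and leaves this unclear. Run the full imputation code on blinded data with dummy treatment codes before lock, so that process problems surface while a change is still harmless.

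As an optional extra, fix a larger total number of imputations whatever the non-monotone rate, for example at least 500. This shrinks dependence on the seed but does not remove it.

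The core change costs one SAP edit. More imputations cost computing time, including for the leave-one-site-out and subgroup runs. The tipping-point analysis has 11 shift values per arm; if run as a full grid, that is 11×11 = 121 cells, or 121×500 = 60,500 CMH analyses.

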12.2 Secondary Efficacy Endpoints Analysis

Secondary efficacy endpoints are based on the vIGA-AD scale or EASI questionnaire. The list of secondary efficacy endpoints can be found in Section [2](#) and their derivation in Section [5.5](#).

- For more details about the vIGA-AD scale refers to Section [12.1.1](#).
- For the EASI questionnaire, four anatomic sites (head, upper extremities, trunk, and lower extremities) are assessed for erythema, induration/infiltration (papules), excoriation, and

 Innovaderm Research	STATISTICAL ANALYSIS PLAN, Version 1.0
Protocol Number: ARQ-151-315	Sponsor: Arcutis Biotherapeutics, Inc.

lichenification as seen on the day of the examination. The severity of each sign is assessed using a 4-point scale (half steps are allowed e.g., 0.5): 0 (none), 1 (mild), 2 (moderate), and 3 (severe). The area affected by AD within a given anatomic site is estimated as a percentage of the total area of that anatomic site and assigned a numerical value according to the degree of AD involvement as follows: 0 (no involvement), 1 (1-9%), 2 (10-29%), 3 (30-49%), 4 (50-69%), 5 (70-89%), and 6 (90-100%).

For each secondary efficacy endpoint, missing data will be imputed and data will be summarized as for the primary efficacy endpoint (refer to Section 12.1.3).

Upon successful demonstration of statistical significance for the primary efficacy endpoint, the secondary efficacy endpoints will be tested sequentially at an alpha level of 0.025.

The secondary efficacy endpoint of vIGA-AD success among subjects with vIGA-AD score of ‘Moderate’ at randomization will be analyzed as described for the primary efficacy endpoint (refer to Section 12.1.3) but based on the vIGA-AD Moderate ITT population (refer to Section 4.3) and use of a chi-square test to evaluate the treatment effect. That is, as per the vIGA-AD Moderate ITT population definition all subjects included in this analysis will have a randomized vIGA-AD score of Moderate (3) and so, the CMH test cannot be used.

The remaining secondary efficacy endpoints, comprised of the endpoints of EASI-75 at Week 4, vIGA-AD of ‘clear’ or ‘almost clear’ at Week 4, vIGA-AD of success at Week 2, vIGA-AD of ‘clear’ or ‘almost clear’ at Week 2, vIGA-AD of success at Week 1 and vIGA-AD of ‘clear’ or ‘almost clear’ at Week 1 will be performed as described for the primary efficacy endpoint (refer to Section 12.1.3) based on the ITT population (refer to Section 4.1).

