Continuous exploratory efficacy endpoints will be analyzed at Week 1, Week 2, Week 3 (WI-NRS only), and Week 4 and for daily WI-NRS assessments using an analysis of covariance (ANCOVA) with the factors of treatment, randomized vIGA-AD score, and baseline of the variable under analysis as covariate. The Least Square (LS) mean and its standard error, difference in LS means between treatment group (i.e., active - vehicle), its standard error and associated 97.5% and 95% confidence interval, and p-value for difference from vehicle will be presented at each visit. These analyses will be performed based on observed data in the ITT population.

Exploratory categorical endpoints based on vIGA-AD, EASI, or WI-NRS, ie VIGA-AD score of clear, EASI-50, EASI-75, EASI-90, EASI-100, WI-NRS success in the WI-NRS population, will

 Innovaderm Research ■■■	STATISTICAL ANALYSIS PLAN, Version 1.0
Protocol Number: ARQ-151-315	Sponsor: Arcutis Biotherapeutics, Inc.

be analyzed by visit and treatment group based on MI data and the ITT population with the same methods used for related primary or secondary endpoints. For all categorical exploratory efficacy endpoints, count and percentages of subjects meeting the criteria for exploratory efficacy endpoints will be presented by visit and treatment group based on observed data in the ITT population along with a 97.5% and 95% Wilson CI. The observed data will also be analyzed using a CMH test adjusted for randomized vIGA-AD score. Common MH odds ratio, common MH proportion difference and their common associated 97.5% and 95% CIs, adjusted for the randomized vIGA-AD score, will be provided. The p-value will be from a CMH test, unless the common MH odds ratio is not estimable. In such circumstances, the p-value will be from a MH test for the common MH proportion difference.

The p-values will be nominal as no formal inferential testing will be done on exploratory efficacy endpoints.

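### Replacing the CMH p-value with a Sato-variance difference test when the odds ratio is not estimable is unnecessary, and it can raise the Week 1 vIGA-AD success test from 2.5% to about 6%

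*SAP*

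**What the plan says.** SAP 6.2.1, step 3c(i), pools the CMH statistics over the imputed datasets after a Wilson-Hilferty transformation and states: "This p-value will be the primary p-value used to evaluate the result according to the multiple testing strategy described in Section 6.5". Step 3c(ii) then sets that p-value aside. The condition is "Should the common MH odds ratio from the analysis of at least one of the multiply-imputed datasets be not estimable"; the combined odds ratio is then withheld, and the conclusion is taken from a pooled test of the MH proportion difference with Sato variance. There are 25 to 250 imputed datasets, and one is enough.

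Section 12.1.3 repeats the rule for the primary endpoint: "Should the odds ratio be not estimable for at least one multiply imputed dataset, the conclusion of" the study passes to the MH proportion-difference test. For the six secondaries other than the Moderate one, section 12.2 says the analysis "will be performed as described for the primary efficacy endpoint (refer to Section 12.1.3) based on the ITT population". Section 12.3 does the same for nominal exploratory p-values: "The p-value will be from a CMH test, unless the common MH odds ratio is not estimable".

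Section 12.1.3 speaks of Week 4 only. That the switch also governs the Week 1 and Week 2 endpoints is a reading of step 3c, which is written for every analysis, together with section 12.2. It is the natural reading. The SAP does not define when an odds ratio is not estimable.

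**The concern.** A non-estimable odds ratio is a problem of estimation, not of testing. It arises when vehicle has no responders (infinite odds ratio) or, because the odds ratio is log-transformed before pooling, when active has none. In both cases the CMH statistic can still be computed. If neither arm has a responder, the Sato test is undefined too, so the fallback rescues nothing.

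The replacement test is weakest exactly where it is called on. An arm with no responders adds nothing to the estimated variance of the difference, so an empty vehicle arm makes that variance too small under the null.

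The secondaries are tested in fixed order with a stated familywise error of 0.025. The endpoint most likely to meet the rule is vIGA-AD success at Week 1. It requires clear or almost clear plus a 2-grade improvement by about Day 8, so a child who starts at Mild must be fully clear. Very few responders are plausible there, and the switch would then decide a formal claim.

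**Working it through.** **Inputs.** From the documents: 433 active and 217 vehicle subjects (protocol synopsis), about 490 of the 650 Moderate, two-sided alpha 0.025 (critical z 2.2414, chi-square 5.02). Assumed: the Week 1 success rate, because the 22% and 37-38% in the sample size section are Week 4 figures.

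**The plan's own figure.** Power at 37% against 22%: pooled rate (433 × 0.37 + 217 × 0.22)/650 = 0.3199; null SE 0.03880; alternative SE 0.03646; z = (0.15 − 2.2414 × 0.03880)/0.03646 = 1.73; power 95.8%. The same formula with 327 and 163 Moderate subjects gives 88.2%. The stated figures of more than 90% and more than 80% reproduce.

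**One table, both tests.** Let a and b be the responders among n1 = 433 and n2 = 217, N = 650, in a single stratum with complete data.

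- CMH = (N − 1)(a·n2 − b·n1)² / [n1·n2·(a + b)(N − a − b)].
- Sato variance = (d·P + Q)/w², where d = a/n1 − b/n2, w = n1·n2/N, P = [n1²·b − n2²·a + n1·n2(n2 − n1)/2]/N² and Q = [a(n2 − b) + b(n1 − a)]/(2N).

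For 5 against 0:

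- d = 0.011547, P = −24.576, Q = 0.8346, w = 144.555. The variance is (−0.2838 + 0.8346)/144.555² = 2.636 × 10⁻⁵, so z = 0.011547/0.005134 = 2.249 and p = 0.0245.
- CMH = 649 × (5 × 217)²/(433 × 217 × 5 × 645) = 2.521, p = 0.112.

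The active arm's own binomial variance, 0.011547 × 0.988453/433, is also 2.636 × 10⁻⁵, so the Sato variance contains nothing from vehicle. The pooled null variance, (5/650)(645/650)(1/433 + 1/217) = 5.28 × 10⁻⁵, is twice as large.

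| Active vs vehicle responders | Fallback p | CMH p | CMH p, Wilson-Hilferty |
|---|---|---|---|
| 5 vs 0 | 0.0245 | 0.112 | 0.108 |
| 9 vs 0 | 0.0024 | 0.033 | 0.031 |
| 10 vs 0 | 0.0014 | 0.024 | 0.023 |

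From 5 to 9 active responders against none, the fallback is significant and CMH is not.

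**Size at a common rate of 1%.** The chance of an empty vehicle arm is 0.99²¹⁷ = 11.3%. The chance of at least 5 active responders is 43.6%, and of at least 10 it is 1.3%. With vehicle empty, the fallback rejects with probability 0.113 × 0.436 = 4.92%, CMH with 0.113 × 0.013 = 0.15%. CMH alone has size 1.45%, so the rule gives 1.45 − 0.15 + 4.92 = 6.22%.

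Exact enumeration of both binomials, complete data, with the Wilson-Hilferty CMH p-value:

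| Common rate | Switch if vehicle empty | Switch if either arm empty | CMH kept |
|---|---|---|---|
| 0.5% | 3.5% | 2.5% | 1.3% |
| 1% | 6.2% | 5.8% | 1.45% |
| 1.5% | 4.3% | 4.2% | 1.8% |
| 2% | 2.8% | 2.8% | 2.1% |
| 3% | 2.4% | 2.4% | 2.4% |

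The peaks are 6.27% at a 0.94% rate and 5.84% at 0.99%. Size exceeds 2.5% only for rates of 0.41-2.24% (vehicle-empty reading) or 0.50-2.24% (either-arm reading). At 1%, false claims in favour of active are 4.9% under the rule and 0.15% with CMH kept; nominal is 1.25% per direction. Without the borderline 5 vs 0 table, size at 1% is 4.3% or 3.9%. Enumeration over the two strata also gives 6.2% and 5.8%.

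**Missing data.** The effect depends on where imputed values come from. The PMM step uses "the treatment group, and vIGA-AD score outcomes at previous visits" as regressors but names no donor set. In the MCMC step for intermediate visits, "the model will include the vIGA-AD scores at baseline, Week 1, Week 2, and Week 4", with no treatment term. Simulated size at a 1% rate (vehicle-empty trigger, Week 1 missing completely at random, 25 imputations, Rubin pooling, 60,000 trials per cell):

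| Donors | 3% missing | 5% missing | 10% missing |
|---|---|---|---|
| Same arm and stratum | 6.3% | 6.2% | 6.1% |
| PMM on treatment and baseline, donors can cross arms | 5.1% | 4.7% | 3.4% |
| Pooled over arms within stratum | 4.4% | 3.7% | 2.1% |

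With the either-arm trigger the rows are 5.8/5.7/5.6%, 4.7/4.2/2.9% and 3.9/3.1/1.7%. CMH kept gives 1.1-2.0% in these settings. The PMM row needs an assumed Week 1 score distribution; two other assumed distributions gave 5.4-5.5% at 3% missing and 4.7-5.0% at 5%. The MCMC step was not simulated, so the three schemes are not a strict bracket. At a 2% rate the rule gives 2.1-3.6% (vehicle-empty trigger); at 3%, rule and CMH differ by at most 0.1 points.

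**The case against.** The strongest reply concerns reach. No Week 1 rate is documented, the excess exists only in a narrow band, and 6% is close to the maximum with complete data. A false claim needs the primary and five earlier secondaries rejected, including both Week 2 endpoints, and no true effect at Week 1. If active is even slightly better at Week 1, a rejection in its favour is not a type I error. With missing data the figure at 1% runs from 1.7% to 6.3%, and some imputation schemes leave no excess. All of this stands. It limits the size of the problem but gives no reason to keep the switch.

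The second reply is that the proportion difference is the SAP's supportive summary, so turning to it is transparent, while CMH is conservative here: of its 1.45% size at a 1% rate, about 1.3 points favour vehicle and only 0.15 favour active. The conservatism is real. It does not justify 4.9% in that direction against a nominal 1.25%.

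Third, the non-responder and observed-data CMH analyses planned for this endpoint (SAP 12.2, Table 5) would probably show the conflict. They would, but they do not decide the claim.

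**Conclusion.** The concern holds. The switch is unnecessary wherever one arm has a responder, and with an empty vehicle arm it rejects too easily. For Week 1 vIGA-AD success, once testing reaches it, size is about 6% near the worst case (complete data, both arms at an assumed 1%). It is above 2.5% only for common rates of roughly 0.4% to 2.2%, and usually lower with missing data. Trial-wide error is smaller by the chance of reaching that step. The primary and the Moderate Week 4 endpoint are unaffected at the planned rates: at 22%, an empty vehicle arm has probability 0.78²¹⁷, below 10⁻²³. This is a point to consider, not one that threatens the main conclusion.

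**What to change.** Remove the switch as a decision rule in SAP 6.2.1 step 3c(ii) and in 12.1.3. Suggested text:

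> If the common MH odds ratio cannot be estimated in one or more imputed datasets, the combined odds ratio and its CIs are not presented, and the common MH proportion difference is given as the estimate only. The decision p-value remains the multiple-imputation CMH p-value of step 3c(i) (for the vIGA-AD Moderate ITT endpoint, the multiple-imputation chi-square p-value). If any imputed dataset has no responders in both arms combined, the endpoint is declared not statistically significant.

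The Moderate endpoint is named separately because it "will be assessed with an unstratified chi-square test". For consistency, section 12.3 should keep the nominal CMH p-value when the odds ratio is not estimable and give none if neither arm has a responder.

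The cost is SAP wording; the step 3c(i) p-value is already produced. The downside is power when responders are very few. With complete data and assumed active/vehicle rates, it falls from 50% to 20% at 2%/0.3%, from 33% to 14% at 2%/0.5% and from 48% to 42% at 3%/0.5%, and stays at 70% at 5%/1%. Part of that lost power comes from a test that does not hold its level.
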